- Smoking
- Diabetes
- Urinary tract infection history
- Current medication use

Physical Examination

- Height and weight

Surgery should be scheduled and performed within 4 months. If more than 4 months transpires before surgery, baseline instruments will need to be re-administered.

H. Randomization

After eligibility is determined and consent is obtained from the participant, the participant will be randomized to one of the two treatment arms using a web-based randomization system. To minimize any risk of selection bias resulting from clinician knowledge of current or future treatment assignments, each participant will be randomized by the surgeon when the participant is in the operating room. The participant will be randomized to one of two apical procedures: either a vaginal hysterectomy with USLS or mesh strap vaginal hysteropexy (Uphold® procedure), with the randomized procedure provided to the surgeon for each participant individually in the operating room immediately prior to the surgery. Other native tissue vaginal wall prolapse repairs (e.g., anterior colporrhaphy, posterior colporrhaphy, perineorrhaphy) will be allowed as needed.

Randomization (1:1 to the two treatment arms) will be performed using permuted blocks, with a block size that is known only to the DCC and will be stratified by site. For each participant, the web-based system will determine the treatment allocation from a static randomization table developed by the study randomization statistician prior to the start of the study. Only the study

statistician and randomization system programmer will have access to the randomization table to minimize the risk of selection bias.

I. Appointment Scheduling

Routine clinical practice postoperative visits will take place during the 12 week postoperative period with the inclusion of one study visit at 6 weeks to assess for early outcomes. The 6 week in person visit and the in person visits every 6 months for the duration of the study will capture the following outcomes:

- 1) Urinary function including duration of post-op catheterization and de novo voiding dysfunction rates. A PVR will be assessed by catheterization or bladder scan at the 6 week visit and this is defined as an elevated postoperative post void residual > 150 ml that was not present preoperatively.
- 2) De novo incontinence rates and severity assessed by the UDI-6, ISI, and AE survey
- 3) Functional activity by administration of the Functional Activity Assessment Scale⁴²

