Postoperative recovery#			X										
POPQ	X			X	X	X	X	X	X	X	X	X	X
AE review		X	X	X	X	X	X	X	X	X	X	X	X
Exam for mesh exposure			X	X	X	X	X	X	X	X	X	X	X
PFDI – Question 3	X		X	X	X	X	X	X	X	X	X	X	X
Functional Activity Scale	X		X	X	X	X	X		X		X		X
Surgical Pain Scale	X		X	X	X	X	X		X		X		X
PFDI-20 (includes POPDI-6, CRADI-8, UDI-6)	X		X	X	X	X	X		X		X		X
PFIQ	X			X	X	X	X		X		X		X
PGI-I				X	X	X	X		X		X		X
ISI	X		X	X	X	X	X		X		X		X
PISQ-IR	X			X	X	X	X		X		X		X
BIS	X		X	X	X	X	X		X		X		X
SF-12	X			X	X	X	X		X		X		X

* Includes OR complications with Dindo score, EBL, Transfusion, HGB change from pre-op to POD1, length of hospital stay.

Assess duration of postoperative catheterization, PVR, de novo incontinence, pelvic pain scale and pain mapping review for vagina, groin, and leg pain.

M. Outcome Measures

The following outcome measures will be collected at baseline, 6 months, 12 months, and then every 6 months with the survival analysis approach.

M.1 Primary Outcome Measure

A participant will be considered a treatment failure if any ONE of the following criteria is met:

- 1) Report of bothersome vaginal bulge symptoms (see definition below), or
- 2) Re-treatment for prolapse (surgery or pessary), or

Confidential Please Do Not Copy

- 3) Any prolapse measure (Ba, C, Bp) is beyond the hymen (i.e. > 0 cm)

Bothersome vaginal bulge symptoms = positive response to Question 3 of the PFDI-20: “Do you usually have a bulge or something falling out that you can see or feel in your vaginal area?” AND any degree of bother. This single question has been identified to most accurately and reliably identify those women with POP. An affirmative answer to this question was 96% sensitive (95%CI 92-100) and 79% specific (95%CI 77-92) for prolapse beyond the hymen. The 1-week test-retest reliability was good (kappa .84).⁴⁷

Participants not considered a treatment failure for the primary outcome will be considered a treatment success.

M.2 Comparative Secondary Outcome Measures

Secondary Aim 1 – Secondary Efficacy Outcomes: These measures will require a statistical analysis plan and will be reported in the primary outcome manuscript.

- 1) Anatomic: POPQ point (Ba, Bp, C), mean or median (but should be normally distributed) measures postop in each group. Proportion of participants in each group with C > -1/2 TVL.
- 2) Functional:
 - a) Prolapse – mean Patients Global Impression of Improvement (PGI-I)⁴⁸, mean overall prolapse symptoms using POPDI-6⁴⁹ scores

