 - e. Sexual functional measures obtained at 6-month post-operative time points including:
 - i. PISQ-IR scale measures
 - ii. Risk of de novo dyspareunia
 - f. Bowel function obtained at 6-month post-operative time points using CRADI-8 scores

- g. Quality of Life (QO)L measures obtained at 6-month post-operative time points including:
 - i. General SF-12 physical component and mental component scales
 - ii. Pelvic QOL as measured by PFIQ total score and three subscales
 - iii. Functional activity as measured by the Activity Assessment Scale
- 3. Safety and tolerability of the two treatment regimens:
 - a. Intraoperative safety measured in each of the treatment arms including:
 - i. Operative time
 - ii. Estimated blood loss
 - iii. Proportion of participants with blood transfusion
 - iv. Intra- and post-operative complications categorized using a modification of the Dindo Classification.
 - b. Risk of adverse events on the two treatment arms as measured by proportion of participants with any of the following events:
 - Mesh related complications: mesh exposure in the vagina or mesh erosion into another organ; note that level of complication will be characterized into based on the following response classification schema: (a) None or nonsurgical medical intervention only; (b) Minor or intra-office surgical intervention; (c) Outpatient surgery; (d) Inpatient surgery
 - ii. Rates of pain captured from the modified Surgical Pain Scale, pain medication use, and location of pain with Pain Mapping Instrument.
 - iii. Pelvic infection
 - iv. Risk of perioperative infections
 - v. Risk of urinary tract infections
 - vi. Vaginal infections with flora uncommon to the vaginal canal
 - vii. Risk of any of De novo vaginal bleeding, atypical vaginal discharge, fistula formation, neuromuscular problems (including groin and leg pain)
 - viii. Need for subsequent procedures- Any surgical or non-surgical treatment for pelvic floor disorders (including urinary incontinence, voiding dysfunction, defecatory dysfunction or fecal incontinence, recurrent prolapse, and dyspareunia/pelvic pain). Any subsequent uterine or cervical office or Operating Room procedure in hysteropexy group (e.g., cervical biopsy, LEEP, hysteroscopy, D and C, hysterectomy).
 - ix. Subsequent uterine or cervical pathology
 - x. Risk of vaginal scarring defined as: De novo vaginal scar requiring medical or surgical intervention, or adversely affecting quality of life.

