PISQ-IR not sexually active – partner related subscale score change from baseline	Continuous	The PISQ-IR not sexually active – partner related subscale score will be computed at 6- month intervals using standard scoring algorithms. Specifically, sum the scores for questions Q2a, Q2b (1=strongly agree, 4=strongly disagree). If there is more than 1 missing response then a total score is not calculated. To handle missing values, the final score is obtained by dividing the sum by the number of items answered. The outcome will then be computed as the difference in score at Month 1 and the score at baseline. If data at any month are missing, the outcome variable will be coded as missing. Scores should only be calculated for participants that are not sexually active.
PISQ-IR not sexually active – condition specific subscale score change from baseline	Continuous	The PISQ-IR not sexually active – condition specific subscale score will be computed at 6-month intervals using standard scoring algorithms. Specifically, sum the scores for questions Q2c, Q2d, Q2e (1=strongly agree, 4=strongly disagree). If there is more than 1 missing response then a total score is not calculated. To handle missing values, the final score is obtained by dividing the sum by the number of items answered. The outcome will then be computed as the difference in score at Month 1 and the score at baseline. If data at any month are missing, the outcome variable will be coded as missing. Scores should only be calculated for participants that are not sexually active.

Variable	Туре	Definition
PISQ-IR not sexually active – global quality subscale score change from baseline	Continuous	The PISQ-IR not sexually active – global quality subscale score will be at 6-month intervals using standard scoring algorithms. Specifically, sum the scores for questions Q4a, Q4b, Q5a, and Q6 using reverse scores for all but Q5a (Q4a and Q4b are likert scales of 1 to 5; Q5a: 1=strongly agree, 4=strongly disagree; Q6: 1=Not at all,, 4=a lot). If there are more than 2 missing responses then a total score is not calculated. To handle missing values, the final score is obtained by dividing the sum by the number of items answered. The outcome will then be computed as the difference in score at Month 1 and the score at baseline. If data at any month are missing, the outcome variable will be coded as missing. Scores should only be calculated for participants that are not sexually active.

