PISQ-IR not sexually active – condition impact subscale score change from baseline	Continuous	The PISQ-IR not sexually active – condition subscale score will be computed at 6-month intervals using standard scoring algorithms. Specifically, sum the scores for questions Q3, Q5b, Q5c using reverse scores for Q3 (Q3: 1=Not at all,,4=a lot; Q5b, Q5c: 1=strongly agree, 4=strongly disagree). If there is more than 1 missing response then a total score is not calculated. To handle missing values, the final score is obtained by dividing the sum by the number of items answered. The outcome will then be computed as the difference in score at Month 1 and the score at baseline. If data at any month are missing, the outcome variable will be coded as missing. Scores should only be calculated for participants that are not sexually active.
PISQ-IR sexually active – arousal, orgasm subscale score change from baseline	Continuous	The PISQ-IR sexually active – arousal, orgasm subscale score will be computed at 6- month intervals using standard scoring algorithms. Specifically, sum the scores for questions Q7, Q8a, Q10, and Q11 using reverse scores for Q11 (Q7, Q8a, Q11: 1=never, ,5=[almost] always; Q10: 1=much less intense,5=much more intense; check box response to Q11 = 1). If there are more than 2 missing responses then a total score is not calculated. To handle missing values, the final score is obtained by dividing the sum by the number of items answered. The outcome will then be computed as the difference in score at Month 1 and the score at baseline. If data at any month are missing, the outcome variable will be coded as missing. Scores should only be calculated for participants that are sexually active.

Variable	Туре	Definition

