PISQ-IR sexually active – global quality rating subscale score change from baseline	Continuous	The PISQ-IR sexually active – global quality rating subscale score will be computed at 6- month intervals using standard scoring algorithms. Specifically, sum the scores for questions Q19a-Q19c, Q20a using reverse scores for Q19a-Q19c (Q19a-c: 1=satisfied,5=dissatisfied; Q20a: 1=strongly agree,,4=strongly disagree). If there are more than 2 missing responses then a total score is not calculated. To handle missing values, the final score is obtained by dividing the sum by the number of items answered. The outcome will then be computed as the difference in score at Month 1 and the score at baseline. If data at any month are missing, the outcome variable will be coded as missing. Scores should only be calculated for participants that are sexually active.
Risk of de novo dyspareunia defined at 6-month post- operative intervals (aggregated across post- surgical reporting period)	Binary	Defined via two different mechanisms: (a) as an event of dyspareunia as listed on AE form or the 6-month complication evaluation form; or (b) assessed via reporting on the PISQ-IR instrument. Note that because on masked review women moved in and out of the dyspareunia category after surgery, the decision was made to evaluate all incidents of dyspareunia irrespective of de novo status.
Bowel function as measured by the PFDI-SF Colorectal- Anal Distress Inventory scale at 6-month post-operative intervals	Continuous	The PFDI-SF Colorectal-Anal Distress Inventory (CRADI) scale will be computed at 6 month post-operative intervals using standard scoring algorithms described by Barber (2006) to create a measure scaled 0 to 100 at each time point. If data at any month are missing, the outcome variable will be coded as missing for that month. All longitudinal analyses or time-specific analyses will use all available data.

Variable	Туре	Definition
Physical component summary scale from SF-12 (PCS-12) at 6-month post- operative intervals	Continuous	PCS-12 will be computed at 6 month post-operative intervals using standard algorithms from the SF-12 developer. If data at any month are missing, the outcome variable will be coded as missing for that month. All longitudinal analyses or time-specific analyses will use all available data.

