9.4 Secondary Efficacy Analysis Methods

9.4.1 General Approach

As outlined in the above sections, the secondary outcome variables comprise a combination of binary, ordinal, and continuous measures that are collected at 6-month intervals through post-operative Month 24 and at either 6- or 12-month intervals thereafter. These outcome measures will be summarized in both tabular and graphical fashion by treatment arm over the full follow-up period, although the focus of the analysis will be on the first 36 months of the post-operative period. We will then use model-based approaches appropriate for the variable type (linear mixed models for continuous variables and GEE extensions of robust Poisson regression models for binary outcomes) to compare the outcomes for the two treatment arms across time.

Because the primary scientific interest for the study is in the trajectories of various the outcomes across time and because information about the patterns of these trajectories is limited, a longitudinal approach incorporating all time points will generally be employed. Specifically, the unit of analysis will be the participant visit, where visits are defined as in Section 4.5 starting 6 months post operatively, and the models will incorporate treatment group, time, and treatment group by time, as well as site, the randomization stratification variable, as fixed effects in the model with time (or visit) will be treated as a categorical variable to incorporate the expected non-linearity of time effects. Participant will be included as a random effect in the linear mixed model with an assumed compound symmetric covariance structure across the post-operative observation period and this same compound symmetric structure will be assumed in the GEE model with observations clustered within participant. The general structure of the SAS code that will be used for the mixed model (using the POPDI-6 as an example) is summarized below.

Proc Mixed data=SUPeR;

WHERE visit le 36; *** Constrains analysis to first 36 months of follow-up;
Class treatment visit center participant;
Model POPDI-6=treatment visit treatment*visit center/solution;
Random participant;
Lsmeans treatment*visit/ pdiff Cl;
Contrast 'POPDI Outcome' treatment 7 -7 treatment*month 111111111-1-1-1-1-1;

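### All ten PISQ-IR change-from-baseline variables in SAP 9.2 use a Month 1 assessment that is not scheduled, against the 6-month timing in the same rows and in SAP 3.2 and 9.4

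*SAP*

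**What the plan says.** SAP 9.2 lists ten PISQ-IR subscales as continuous secondary efficacy outcomes, each labelled a change from baseline, for example "PISQ-IR not sexually active – condition impact subscale score change from baseline" and "PISQ-IR sexually active – global quality rating subscale score change from baseline". Each row first puts scoring on a 6-monthly footing, as in "partner related subscale score will be computed at 6- month intervals using standard scoring algorithms". It then gives the scoring rule and defines the outcome: "The outcome will then be computed as the difference in score at Month 1 and the score at baseline". A last rule says the outcome is missing if data at any month are missing.

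Other parts of the plan give a different timing:

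- SAP 3.2, item 2e: "Sexual functional measures obtained at 6-month post-operative time points including" the PISQ-IR scales and de novo dyspareunia.
- SAP 9.4.1 takes the participant's visit as the unit of analysis, where "visits are defined as in Section 4.5 starting 6 months post operatively". SAP 9.4.3 names the PISQ scales among the continuous outcomes handled this way.
- Protocol section I provides, among routine post-operative care, for "the inclusion of one study visit at 6 weeks to assess for early outcomes".
- The PISQ-IR row of Protocol Table 4 reads "PISQ-IR X X X X X X X X" once its blank cells are dropped. The SAP schedule table agrees.

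**The concern.** The defining sentence of all ten variables points to an assessment that the trial does not make. A programmer following SAP 9.2 to the letter would get an empty column for each. A programmer who sees the slip must supply a visit, and SAP 9.2 does not say which.

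Sexual function is a named part of Secondary Aim 1, and Protocol M.2 says the Aim 1 measures will be reported in the primary outcome manuscript. Change in PISQ-IR is also one side of the Aim 5 correlation with change in body image (SAP 9.4.6). The SAP's display pages carry the date 12/15/2018, after the February 16, 2018 cut-off for the first lock in SAP 4.4.2. A choice of visit, metric or missing-data rule made at programming would therefore be made with the 36-month data already collected.

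**Working it through.** No power, alpha or sample-size figure depends on this point. The check is a count, a comparison with the schedule, and a window calculation.

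**1. Rows affected (SAP 9.2).** Not sexually active: partner related, condition specific, global quality, condition impact = 4. Sexually active: arousal/orgasm, condition specific, partner related, desire, condition impact, global quality rating = 6. Total 4 + 6 = 10, and all ten carry the Month 1 sentence.

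**2. PISQ-IR schedule (Protocol Table 4; SAP schedule table).** There are eight marks: baseline plus 6, 12, 18, 24, 36, 48 and 60 months. The 6-week, 30-, 42- and 54-month cells are blank. Neither table has a Month 1 column.

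**3. Could a visit window reach Month 1?** SAP 7.9 allows ±6 weeks around the 6-monthly visits. One month is 365.25 / 12 / 7 ≈ 4.35 weeks.

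- Month 1 ≈ 4.3 weeks.
- The 6-month visit is at 6 × 4.35 ≈ 26.1 weeks. Its window opens at 26.1 − 6 = 20.1 weeks, which is 20.1 / 4.35 ≈ 4.6 months.
- The 6-week visit is at 6 / 4.35 ≈ 1.4 months and has no PISQ-IR.

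No PISQ-IR window contains Month 1, so the number of Month 1 change scores that can be derived is 0 of 10.

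**4. What the rest of the plan supports.** With each scheduled visit in place of Month 1, every subscale has 7 post-operative change scores (6, 12, 18, 24, 36, 48, 60 months). Five of these (6, 12, 18, 24, 36) fall within the 36-month focus of SAP 9.4.1.

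**5. Missing-data wording compared across SAP 9.2.**

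| Scales | Missingness limited to the month | States that all available data are used |
|---|---|---|
| POPDI, UDI, CRADI, SF-12, CRAIQ-7, POPIQ-7, PFIQ total, AAS | yes | yes |
| UIQ-7 | no | yes |
| Ten PISQ-IR subscales | no | no |

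**6. Score or change.** SAP 9.2 labels the PISQ-IR outcomes as change from baseline. Protocol M.2 speaks of mean PISQ-IR, SAP 3.2 of scale measures, and the example model in SAP 9.4.1 takes the visit score as response with no baseline term. The choice affects precision, which depends on a baseline-to-follow-up correlation the documents do not give. It also affects who contributes. Each subscale is scored only for women in the matching sexual-activity group, so a change score needs the same status at both assessments and a visit score does not.

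**7. Aim 5.** SAP 9.4.6 correlates change in BIS with change in PISQ but names no visit and does not define the change. The only PISQ-IR change definition in the SAP is the Month 1 one. BIS is collected at all seven post-operative PISQ-IR visits (and at 6 weeks), so seven visits could supply the pair.

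**The case against.** The strongest defence is that the SAP's intent can be recovered. The same rows, SAP 3.2 and SAP 9.4.1 all point to 6-monthly scores, and SAP 9.4.1 already fixes a model with visit as a categorical term and a treatment contrast across 36 months. Choosing one visit for that comparison would contradict it. SAP 7.7 calls all secondary analyses exploratory, and SAP 9.4.3 calls the functional ones descriptive. This stands, and it limits the weight of the point. It does not make the Month 1 sentence correct.

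Three stronger readings are tempting, and the documents support none of them.

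- *The sexual-function objective cannot be computed.* Scores at each visit can be analysed under SAP 9.4.1 and 9.4.3. Dyspareunia, the other sexual-function outcome, is defined without any Month 1 term. Only the change-score derivation fails.
- *One missed visit voids a woman's whole PISQ-IR outcome.* For a difference between two scores, missing data at any month can simply mean that one of those two scores is missing. The UIQ-7 row drops the same limiting phrase yet keeps all available data, which suggests loose drafting. What survives is that the PISQ-IR rows are less precise than their neighbours.
- *A visit was chosen after seeing results.* The date in the SAP shows only that data had been collected. SAP 4.4.2 and 7.5 describe masked decisions, and nothing reports that a visit was picked.

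On Aim 5, it is fair to say that SAP 9.4.6 does not refer to the SAP 9.2 variables. The correlation is therefore not impossible. It is unspecified as to visit, and the one definition on offer is unusable.

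**Conclusion.** The point holds as a contradiction within the SAP, of moderate severity and wrong as written. Ten of ten PISQ-IR change variables depend on an unscheduled assessment, and none can be derived literally. The plan does not settle three linked choices: the visit or visits for the change score, whether score or change is modelled, and which visit or visits enter the Aim 5 correlation. The primary outcome, its test, alpha and the sample size are unaffected, and no data are lost.

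This rests on two assumptions: that the schedule tables are complete for PISQ-IR, and that the PISQ-R named in SAP 9.4.3 and 9.4.6 is the PISQ-IR. That Month 1 is a carried-over or mistyped label is plausible, but the documents do not say so.

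**What to change.** In SAP 9.2, in all ten rows:

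1. Replace the Month 1 sentence with a rule that, at each scheduled PISQ-IR visit (6, 12, 18, 24, 36, 48 and 60 months, per the schedule table), change is that visit's score minus the baseline score.
2. Reword the missing-data rule so that a missing score makes the outcome missing for that month only and all other available data are used, as for the PFDI-SF scales.

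Then add two statements:

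3. In SAP 9.4.1 or 9.4.3, whether the PISQ-IR model takes the visit score or the change from baseline as its response.
4. In SAP 9.4.6, which visit or visits the correlation of PISQ-IR change with BIS change uses.

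The text of Protocol section K omits 18 months from its list for secondary measures, while both schedule tables include it. The new wording should therefore cite the table.

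The cost is ten edited table rows and two added sentences. No new data are needed. SAP section 14, still to be completed, is the place to record the correction and its date.
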